1.3 Unanticipated Problem

The Office for Human Research Protections considers unanticipated problems to be any incident, experience, or outcome that meets *all* of the following criteria:

- Is unexpected in terms of nature, severity, or frequency given a) the research procedures that are described in the protocol-related documents, such as the Institutional Review Board (IRB)-approved research protocol and informed consent, and b) the characteristics of the subject population being studied;
- Is related or possibly related to participation in the research (possibly related means there is a reasonable possibility that the incident, experience, or outcome may have been caused by the procedures involved in the research); and
- Suggests that the research places subjects or others at **a greater risk of harm** (including physical, psychological, economic, or social harm) than was previously known or recognized.

Expected adverse events may become unanticipated problems if they occur at a greater frequency or severity than was previously expected for an individual subject, as detailed in Section 17 of the protocol.

An incident, experience, or outcome that meets the 3 criteria above will generally warrant consideration of substantive changes in order to protect the safety, welfare, or rights of subjects or others. Examples of corrective actions or substantive changes that might need to be considered in response to an unanticipated problem include the following:

- Changes to the research protocol initiated by the investigator prior to obtaining IRB approval to eliminate apparent immediate hazards to subjects.
- Modification of inclusion or exclusion criteria to mitigate the newly identified risks.
- Implementation of additional procedures for monitoring subjects.
- Suspension of enrollment of new subjects.
- Suspension of research procedures in currently enrolled subjects.

- Modification of informed consent documents to include a description of newly recognized risks.
- Provision of additional information about newly recognized risks to previously enrolled subjects.

Per the definition, only a subset of AEs would be further characterized as unanticipated problems. Additionally, there are other sorts of events that, while not AEs, would also be characterized as unanticipated problems (e.g., contaminated investigational product).

1.4 Protocol Deviation

The Office of Human Subjects Research Protection defines a protocol deviation as any change, divergence, or departure from the IRB approved research protocol.

A serious protocol deviation is a deviation that “meets the definition of a serious adverse event or if it compromises the safety, welfare, or rights of subjects or others.” More specifically, a deviation is serious if it meets any of the following criteria:

- Has harmed or poses a significant or substantive risk of harm to the research subject
- Compromises the scientific integrity of the data collected for the study
- Is a breach of human subject protection regulations, or NIH policies or procedures
- Involves serious or continuing non-compliance with applicable federal, state, local or institutional human subject protection laws, regulations, or policies, or procedures
- Is inconsistent with the NIH Human Research Protection Program’s research, medical, and ethical principles.

Protocol deviations will be reported to the IRB and NIDCR Clinical Director as described in protocol Section 15.5.

2 EVENT CHARACTERISTICS

2.1 Severity of AE/SAEs

The severity of AE/SAEs will be graded according to the National Cancer Institute's Common Terminology Criteria for Adverse Events (CTCAE), Version 4.0. The CTCAE provides a standard framework for recording, analyzing, and reporting events. Following CTCAE convention, AE/SAEs will be graded on a 5-point scale. If the severity of an event cannot be graded using CTCAE convention, the following guidelines will be used:

1. Mild: no intervention required
2. Moderate: minimal, local, or noninvasive intervention
3. Severe: significant symptoms requiring invasive intervention
4. Life-threatening: need for intensive care or emergent invasive procedure
5. Death: resulting from an adverse event

2.2 Relationship to the Investigational Product

For all AEs, the investigator will determine the degree to which an event may have been caused by the investigational product. "Relationship to the investigational product" is a factor used to guide SAE reporting to FDA. The investigator's assessment will be based on clinical judgment and information available in the study and investigational product documentation (e.g., Risks section of the protocol, Investigator's Brochure or Drug Fact Sheet). Alternative causes such as natural history of the underlying disease, concurrent illness, concomitant therapy, study-related procedures, accidents, and other external factors will also be considered and investigated. The following guidelines will be used to aid this determination:

1. Related (Possible, probable, definite)
 - a. The event is not commonly associated with hypoparathyroidism or with one of the study procedures
 - b. The event is known to occur with administration of the product or similar products
 - c. There is a temporal relationship between product administration and event onset
 - d. The event abates when the investigational product is discontinued

- e. The event reappears upon a re-challenge with the product
2. Not Related (Not related, Unlikely)
- a. The event is commonly associated with hypoparathyroidism or with one of the study procedures
 - b. There is no temporal relationship between product administration and event onset
 - c. An alternate etiology has been established

2.3 Relationship to the Research

For all AEs, the investigator will determine the degree to which an event may have been caused by participation in the research. “Relationship to the research” is a factor used to identify unanticipated problems. An event would be considered related to the research if the investigator believes that it may have been caused by the investigational product, by a study procedure, by another study assessment, or any other aspect of study participation.

Relationship to the research will also partly determine whether a non-AE event might be qualified as an unanticipated problem.

2.4 Expected, Based on the Investigational Product

Serious adverse events that are considered to be at least possibly related to investigational product will be evaluated for expectedness based on the investigational product. For purposes of reporting, the Principal Investigator will be responsible for determining whether SAEs are expected or unexpected based on safety information in the Investigator’s Brochure (or Drug Fact Sheet) and the protocol. An SAE will be considered unexpected if the specificity or severity is not described in the available safety information for the investigational product, published medical literature, the protocol, or the informed consent document.

2.5 Expected, Based on the Study

Potential unanticipated problems (i.e., AEs or other events related to participation in the research that potentially place the subject at greater risk of harm) will be evaluated by the principal investigator to determine whether they were expected, based on the study. This broad definition includes documented risks of HPTH and study procedures and assessments; it also includes

consideration of the nature of the subject population being studied. Events that are expected based on any or all of these considerations are considered to be expected, based on the study. Such events would therefore not be considered UPs, because they would not satisfy the unexpectedness criterion.

3 RECORDING AND REPORTING DETAILS

3.1 All Adverse Events

All AE/SAEs will be recorded from the time written informed consent is obtained until subject withdrawal (for non-treated subjects) and through the conclusion of the HPTH post-stabilization phase (for HPTH treated subjects).

At each study visit, the investigator will inquire about the occurrence of AE/SAEs since the last visit. The principal investigator will also review all source documentation related to inpatient study procedures for evidence of AEs. If subjects exhibit medical symptoms or conditions outside of the purview of the study (e.g., depression), they will be referred to their primary care provider or other appropriate medical personnel. Events will be followed until they return to baseline or until stabilization of the event. Participants who have AEs that are ongoing at the time their study participation ends will be referred to physicians outside of the NIH for care and follow-up.

All AE/SAEs will be captured in CRFs that document the event term, severity, duration, relationship to use of the investigational product, relationship to the research, actions taken in response to the event, and outcome. Potential UPs (i.e., events that are related to the research) will be evaluated for expectedness, based on the study. SAEs related to the investigational product will also be evaluated for expectedness, based on that investigational product.

See Section 17.0 for details of AE annual reporting to the IRB and to the FDA.

3.2 Clinically Significant Laboratory Abnormalities

The principal investigator will evaluate all clinical laboratory results for clinically significant abnormalities and document the evaluation in a CRF. Clinically significant findings (e.g., increase in calcium-citrate ratio to >0.7) will be recorded and reported as AEs regardless of their

association with the use of the investigational product. The principal investigator will follow significant abnormalities until they return to baseline or stabilization.

3.3 SAE & UP Reporting

See Section 17 for details of reporting timeframes for SAEs and UPs to the IRB, Clinical Director, and FDA.

SAEs and UPs will be reported to CROMS product safety via the study specific electronic data capture system. SAEs and UPs should be entered into the EDC within 1 business day of learning of the event. Once submitted, CROMS Product Safety will send a confirmation email to the investigator within 1 business day. The investigator should contact the CROMS product safety if this confirmation is not received. The Product Safety Associate will review the event report, gather additional information from the site, as necessary, and consult with the medical monitor or the physician designee.

Together, this Product Safety Team will determine for SAEs whether there is a reasonable possibility that the event is related to the investigational product and if so, whether the event was expected for the investigational product. The Product Safety Team will also review the intensity of the SAE in order to determine follow-up actions.

24.2 Pre-Screening Questionnaire and Eligibility Checklist

[name] 07-D-0016	Prescreening	Subject ID #:
	Telephone Pre-Screening	

Screening Eligibility Questions

1. [Interviewer] Date of interview: / - /
dd mmm yyyy

2. [Interviewer] What is the subject's gender?

- Male
 Female

3. What is your date of birth? / - / OR Age at time of Pre-Screening
dd mmm yyyy If subject is permanently ineligible for the study or does not provide informed consent, enter Age and leave Date of Birth blank.

4. Have you been diagnosed with hypoparathyroidism by a physician?

- Yes
 No (*Ineligible, skip to end*)

4a. Were you diagnosed at least one year ago?

- Yes
 No (*Ineligible, skip to Q16*)

5. Do you have any of the following health problems?

- | | | |
|-------------------------|------------------------------|---|
| Diabetes |  Yes |  No |
| Celiac disease |  Yes |  No |
| Crohn's disease |  Yes |  No |
| Cushing's syndrome |  Yes |  No |
| Active thyroid cancer |  Yes |  No |
| Seizure disorder |  Yes |  No |
| Osteoporosis |  Yes |  No |
| Osteosarcoma |  Yes |  No |
| Paget's disease |  Yes |  No |
| Metastatic bone disease |  Yes |  No |
| Liver disease |  Yes |  No |
| Adrenal insufficiency |  Yes |  No |
| Retinoblastoma |  Yes |  No |
| Li-Fraumeni Syndrome |  Yes |  No |
| Other |  Yes |  No Specify permanently disqualifying condition:  |

If any health problem is Yes, subject is ineligible and skip to end.

6. Are you currently taking any medications?

- Yes

No (*Skip to Q7*)

6a. What medications are you taking?

List medications:

Exclusionary medications: PTH (for more than 2 weeks prior to study entry), thyroid hormone to suppress thyroid stimulating hormone below the assay's detection limit, bisphosphonates, calcitonin, tamoxifen, selective-estrogen receptor modulators, oral or intravenous corticosteroids (>3 weeks in last 6 months), estrogen replacement therapy, or medication for a seizure disorder

6b. [Interviewer] Is the subject taking any exclusionary medications?

Yes (*Ineligible, skip to Q16*)

No

7. Are you allergic to any antibiotics?

Yes

No (*Skip to Q8*)

7a. Which antibiotics are you allergic to?

List antibiotics:

7b. [Interviewer] Were tetracycline antibiotic allergies noted?

Yes (*Ineligible, skip to end*)

No

8. Have you received bone radiation treatment?

Yes (*Ineligible, skip to end*)

No

9. [Females only] Have you been post-menopausal for more than 6 months?

[Removed per protocol amendment]

9a. [Interviewer, Females only] Is the subject peri-menopausal as defined by no menses for 6 months to 5 years?

Yes (*Ineligible, skip to Q16*)

No

10. [Females only] Are you pregnant or breast-feeding?

Yes (*Ineligible, skip to Q16*)

No

11. [Females only] Have you received an injection for birth control in the last 12 months?

Yes (*Ineligible, skip to Q16*)

No

12. [Interviewer] Are there any other reasons to exclude this subject?

Yes (*Ineligible, provide Comment and skip to Q16*)

No (*Skip to Q13*)

12a. Comment on reason or exclusion:

13. [Interviewer] Is the subject eligible for a screening visit?

- Yes
- No (*Skip to Q16*)

14. [Interviewer] Is the subject interested in attending a screening visit?

- Yes
- No (*Skip to end*)

15. [Interviewer] Was an inpatient visit scheduled?

- Yes
- No (*Skip to Q16*)

16. [Interviewer] Will the subject be contacted later to reassess eligibility for the study?

- Yes
- No

Comments associated with this page:

Create

Cancel

[Form Completion Help](#)

Print

[name] 07-D-0016	Inclusion/Exclusion	Subject ID #:
	Inclusion/Exclusion	

Inclusion Criteria

Subjects may only be included if all applicable inclusion questions are answered "Yes".

- | | |
|---|---|
| 1. Adult female aged 18-45 years or adult male aged 18-50 years | [Removed per protocol amendment] |
| 1a. Pre-menopausal female aged 18-45 years or adult male aged 18-70 years |  Yes  No  N/A |
| 1b. Postmenopausal woman aged ≥ 53 years to 70 years and 5 years since last menses |  Yes  No  N/A |
| [2.] Adolescent female with bone age ≥ 14 years (x-ray of the hand and wrist) or adolescent male with bone age ≥ 16 years (x-ray of the hand and wrist) | [Removed per protocol amendment] |
| 3. Physician-diagnosed hypoparathyroidism of at least 1-year duration, confirmed by medical record review |  Yes  No  N/A |
| 4. Intact PTH < 30 pg/mL |  Yes  No  N/A |
| 5. Woman without a uterus with a clinical history of menopause for at least 5 years and an FSH > 30 u/L |  Yes  No  N/A |

Exclusion Criteria

Subjects must be excluded if any responses to questions 1 - 18 are answered "Yes".

- | | |
|--|---|
| 1. Moderate to severe hepatic disease defined as hepatic transaminases (ALT and AST) > 2 times the upper limit of normal |  Yes  No  N/A |
| 2. Severe renal insufficiency defined as a calculated GFR < 25 mL/min/1.73 m ² using the CKD-EPI equation |  Yes  No  N/A |
| 3. Allergy or intolerance to tetracycline antibiotics |  Yes  No  N/A |
| 4. Pregnant or lactating |  Yes  No  N/A |

5. Peri- or post-menopausal as defined by no menses for > 6 months and an FSH > 20 U/L at the screening and/or baseline visits [Removed per protocol amendment]
- 5a. Peri-menopausal defined by no menses for 6 months to 5 years and an FSH > 20 U/L at the screening and/or baseline visits Yes No N/A
6. Chronic diseases that might affect mineral metabolism such as diabetes, celiac disease, Crohn's disease, Cushing's syndrome, or adrenal insufficiency Yes No N/A
7. Concurrent treatment with doses of thyroid hormone intended to suppress thyroid stimulating hormone below the assay's detection limit or persistent thyroid cancer Yes No N/A
- [8.] History of a skeletal disease unrelated to hypoparathyroidism, such as osteoporosis/low bone density (defined as a DXA Z-score or T-score < -2), osteosarcoma, Paget's disease, or metastatic bone disease [Removed per protocol amendment]
- 8a. History of a skeletal disease unrelated to hypoparathyroidism, such as osteoporosis or low bone density (defined as a DXA Z-score < -2 in all subjects or T-score < -2 in subjects ≥ 20 years old), osteosarcoma, Paget's disease, alkaline phosphatase > 1.5 times the upper limit of normal, or metastatic bone disease Yes No N/A
9. History of treatment with bisphosphonates, calcitonin, tamoxifen, selective-estrogen receptor modulators, or directed skeletal irradiation Yes No N/A
10. Use of oral or intravenous corticosteroids for more than 3 weeks within the last 6 months [Removed per protocol amendment]
- 10a. Use of oral or intravenous corticosteroids or estrogen replacement therapy for more than 3 weeks within the last 6 months Yes No N/A
11. Use of depot medoxyprogesterone for contraception within the past 12 months Yes No N/A
12. Chronic inadequate biochemical control with conventional therapy and/or calcium infusion dependent Yes No N/A
13. Seizure disorder requiring antiepileptic medications Yes No N/A
14. Treatment with PTH for more than 2 weeks prior to study entry [Removed per protocol amendment]
- 14a. Treatment with PTH for more than 2 weeks continuously at any time prior to study entry Yes No N/A
15. Any cognitive impairment that limits the subject's ability to comply, independently or through the assistance of a legally authorized representative, with protocol procedures. Yes No N/A

16. Unwillingness or inability to comply with protocol procedures

[Removed per
protocol amendment]

17. History of retinoblastoma or Li-Fraumeni syndrome

Yes No N/A

18. Open epiphyses as determined by an x-ray of the hand and wrist in subjects <21 years of age Yes No N/A

Eligibility Status

Review all responses to the inclusion and exclusion criteria to determine subject eligibility.

19. Is the patient eligible for the study

Yes No

Comments associated with this page:

Submit Query

Cancel

[figure not shown]
Form Completion Help

Print

 Rho

24.3 Study Schema

Effects of HPTH on Bone in Hypoparathyroidism

¹ At this time, subjects will be weaned off HPTH and provided with standard of care medication for a minimum of 3 months (± 2 weeks) and until the subject has stabilized. AE/SAE related to the down titration of HPTH will be reported during this Post-HPTH safety follow-up period. Version Date: 15FEB2011

24.4 Schedule of Events

[name] 07-D-0016: Schedule of Events

	Prescreen	Screening _s	V0	V1	V2	V3	V4	V5	V6	V7	V8	V9	V10 ⁹	V11 ¹⁰
Target Date (months)		2-6	0	6	12	18	24	30	36	42	48	54	60	66
Visit Window (weeks)		±4	±2	±2	±2	±2	±2	±2	±2	±2	±2	±2	±2	±2
Recruitment and Enrollment														
Telephone pre-screening	X													
Informed consent ¹		X												
Medical History														
Medical history		X	X	X	X	X	X	X	X	X	X	X	X	X
Dietician consultation		X	X	X	X	X	X	X	X	X	X	X	X	X
Short Calcium Questionnaire		X	X	X	X	X	X	X	X	X	X	X	X	X
SF-36			X	X	X	X	X	X	X	X	X	X	X	X
Concomitant medications		X	X	X	X	X	X	X	X	X	X	X	X	X
Adverse events		X	X	X	X	X	X	X	X	X	X	X	X	X
Fitness Measures														
Fatigue Symptom Inventory			X	X	X	X	X	X	X	X	X	X	X	X
6-Minute Walk Test			X	X	X	X	X	X	X	X	X	X	X	X
Physical Exam														
Height/weight		X	X	X	X	X	X	X	X	X	X	X	X	X
Vital signs		X	X	X	X	X	X	X	X	X	X	X	X	X
Physical examination		X	X	X	X	X	X	X	X	X	X	X	X	X
Blood Tests														
DNA testing (if indicated)		X												
Chem 20 panel		X	X	X	X	X	X	X	X	X	X	X	X	X
Complete blood count		X	X	X	X	X	X	X	X	X	X	X	X	X
Mineral panel or calcium level ²		X	X	X	X	X	X	X	X	X	X	X	X	X
Thyroid panel		X	X	X	X	X	X	X	X	X	X	X	X	X
25-OH-vitamin D		X	X	X	X	X	X	X	X	X	X	X	X	X
1,25 (OH) ₂ vitamin D ¹¹		X	X	X	X	X	X	X	X	X	X	X	X	X
Intact PTH		X	X	X	X	X	X	X	X	X	X	X	X	X
Bone-specific alkaline phosphate			X	X	X	X	X	X	X	X	X	X	X	X
Osteocalcin			X	X	X	X	X	X	X	X	X	X	X	X
Ionized calcium		X	X	X	X	X	X	X	X	X	X	X	X	X
Research blood samples for storage			X	X	X	X	X	X	X	X	X	X	X	X
24-hr blood sampling ³					X									

	[name] 07-D-0016: Schedule of Events (continued)													
	Prescreen	Screening ⁸	V0	V1	V2	V3	V4	V5	V6	V7	V8	V9	V10 ⁹	V11 ¹⁰
Target Date (months)		2-6	0	6	12	18	24	30	36	42	48	54	60	66
Visit Window (weeks)		±4	± 2	± 2	± 2	± 2	± 2	± 2	± 2	± 2	± 2	± 2	± 2	± 2
Blood Tests														
Acute care and mineral panels ¹¹			X											
FGF23 ¹¹			X											
Urine Tests														
Urine pregnancy test		X	X	X	X	X	X	X	X	X	X	X	X	X
Urinalysis		X	X	X	X	X	X	X	X	X	X	X	X	X
24-hour urine ⁴		X	X	X	X	X	X	X	X	X	X	X	X	X
Spot Urine ¹²			X											
Imaging														
Radiographs to assess bone age ⁵		X												
Renal ultrasound		X	X		X		X		X		X		X	X
DXA ⁶		X	X	X	X	X	X	X	X	X	X	X	X	X
CT of the kidney without contrast			X		X		X		X		X		X	
Quantitative CT (L1 and L2 spine)			X		X		X		X		X		X	
Biopsy														
Baseline bone biopsy			X											
Follow-up bone biopsy ⁷					X		X				X			
PTH														
Conventional care		X											X	X
PTH therapy			X	X	X	X	X	X	X	X	X	X		

¹ Patients enrolled under the previous version of the protocol who are on conventional therapy will re-enter the study at V0 and be re-consented at V0. Patients enrolled under the previous version of the protocol who are on HPTH will re-enter the study during their next scheduled follow-up visit and will be re-consented at that visit.

² Mineral panels and calcium levels may be repeated as needed to monitor response to PTH therapy.

³ Blood will be drawn every 2 hours (± 15 minutes) for 24 hours to measure calcium, magnesium, phosphorus, and albumin.

⁴ At the Screening Visit, single 24-hour urine sample will be collected for calcium, phosphorus, creatinine, magnesium, sodium, citrate, pH, and potassium. At all subsequent visits, two 24-hour urine samples will be collected for the same measurements plus the measurement of N-Telopeptide.

⁵ Radiographs of the hand and wrist to assess bone age will be required for subjects <21 years of age.

⁶ DXA scan of the spine, femur, radius, and total body.

⁷ Subjects will be randomized to receive a single follow-up bone biopsy after 1, 2, or 4 years of HPTH therapy.

⁸ The duration of the screening period will be 2 to 6 months (±1 month) prior to first HPTH dosing.

⁹ At this time point, subjects will have been weaned off HPTH and provided with standard of care medication for a minimum of 3 months (\pm 2weeks) and until the subject has stabilized. Only AE/SAEs related to the weaning/termination of HPTH will be reported during this Post HPTH stabilization phase.

¹⁰ Visit will be completed 6 months after the start of the Post HPTH stabilization phase.

¹¹ Blood draws for an acute care panel, mineral panel, 1,25 (OH)₂ vitamin D, and FGF23 will be completed at 8AM, 12PM, 4PM, and 8PM on the first day of PTH therapy (Day 0). Blood draws for an acute care panel, mineral panel, 1, 25 (OH)₂ vitamin D, and FGF23 will also be collected at 8AM on the second day of PTH therapy (Day 1). One-hour windows are permitted on either side of each specified sampling time.

A morning blood draw will be completed on subsequent in-patient days during V0 for an acute care panel.

¹² Spot urine will be collected for cAMP, creatinine, phosphorus, calcium, and pH at 8AM, 12PM, 4PM, and 8PM on the first day of PTH therapy (Day 0). Spot urine for cAMP, creatinine, phosphorus, calcium, and pH will also be collected at 8AM on the second day of PTH therapy (Day 1). One-hour windows are permitted on either side of each specified sampling time.

A morning spot urine will be collected on subsequent in-patient days during V0 for cAMP, creatinine, phosphorus, calcium, and pH.

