700 apparent increase in wrist fractures¹² or change in cortical porosity¹⁴. The clinical relevance of these
701 changes in radial BMD in hypoparathyroid treated with HPTH is unknown. Thus, this protocol excludes
702 and withdraws subjects with DXA BMD T-scores or Z-scores < -2.

703 Since this study has started, hypocitraturia (defined as a urine calcium to citrate ratio > 0.7 mg/mg) has
704 been observed in many subjects initiation of HPTH therapy. Of note, some subjects also had elevated
705 urine calcium/citrate ratios prior to the initiation of HPTH. Hypocitraturia has not been previously
706 reported in hypoparathyroidism and, to our knowledge, urine citrate has not been assessed in other studies
707 using PTH 1-34 or PTH 1-84 in the treatment of hypoparathyroidism. Thus, the risk of hypocitraturia-
708 associated nephrocalcinosis or nephrolithiasis in this patient population, on conventional or PTH therapy,
709 is not known. The urine calcium/citrate ratio will be monitored throughout the study and subjects will be
710 treated with potassium citrate, as tolerated, as described in section 4.5.5.

711 There is a risk of unforeseen adverse effects with every new drug treatment. The risks of participation are
712 reasonable relative to the significant health benefits and medical knowledge that may be achieved.

713 **8 SUBJECT SAFETY MONITORING**

714 Subjects will be informed that they may choose to withdraw or the investigator may remove them if it is
715 in the subjects' best interest or if the subjects are unable to complete the required assessments. Voluntary
716 withdrawal from the protocol is always an option for the research participants. As described throughout
717 Section 4.5, subjects will have blood and urine measured and evaluated by the study investigators on an
718 ongoing basis, and HPTH dosing will be adjusted according to a standardized dosing algorithm. The
719 principal investigator or designee will evaluate all clinical laboratory results for clinically significant
720 abnormalities and document the evaluation on a CRF. Clinically significant laboratory findings will be
721 recorded and reported as AEs (see Appendix 24.1) regardless of their association with the use of the
722 investigational product.

723 At each study visit, the study investigator will inquire about the occurrence of any AEs since the last visit.
724 The principal investigator will also review all source documentation related to inpatient study procedures

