10. LIST OF PLANNED TABLES

Subject listings associated with the tables below will be provided. Experimental time refers to the baseline, last hPTH treatment, and post-hPTH follow-up visits. Additional tables (eg, those based on the results of sensitivity analysis) will be provided. Other displays, as requested by the PI may be provided as well.

Table Type	Table
Disposition	Summary of Subject Disposition
Demographics	Summary of Study Enrollment by Demographic Characteristics
hPTH Therapy	Summary of the Duration of hPTH Therapy
Primary Efficacy	Summary Statistics of Primary Bone Biopsy Endpoints by Biopsy Year. (Separate tables for Cohorts 2, 3, and Cohort 2 combined with Cohort 3)
	Repeated Measures Analysis of Primary Efficacy Analysis (Separate tables for Cohorts 2, 3, and Cohort 2 combined with Cohort 3)
Secondary Efficacy	Summary of Bone Mineralization Density Assessed by Back-Scattered Electron Imaging by Years of hPTH therapy
	Summary of Biochemical Markers of Bone Metabolism by Experimental Time Including the Statistical Significance of Changes.
	Summary of Blood and Urine Chemistries by Experimental Time Including the Statistical Significance of Changes.
	Summary of Bone Mineralization Density Assessed by DXA and Quantitative CT by Experimental Time Including the Statistical Significance of Changes.
	Summary of Nephrocalcinosis and Nephrolithiasis by Time on Study Drug
	Summary of Fatigue Symptom Inventory and 6-Minute Walk Test by Experimental Time Including the Statistical Significance of Changes.
	Summary of SF-36 Health Survey by Experimental Time Including the Statistical Significance of Changes.
Adverse Events (as provided to DSMB)	Summary of Adverse Events Occurring While on hPTH 1-34 or After Withdrawal from hPTH 1-34
	Summary of Adverse Events Occurring on or after hPTH 1-34
	Summary of Adverse Events Occurring While on Conventional Care
	Summary of Adverse Events for Subjects on Conventional Care
	Summary of Adverse Events Occurring While on hPTH 1-34 or After Withdrawal from hPTH 1-34: Current PI
	Summary of Adverse Events Occurring While on hPTH 1-34 or After Withdrawal from hPTH 1-34: Prior to Current PI
	Summary of Adverse Events Occurring While on Conventional Care: Current PI
	Summary of Adverse Events Occurring While on Conventional Care: Prior to Current PI

	Summary of Adverse Events Occurring While on hPTH 1-34 or After Withdrawal from hPTH 1-34; Related (Unlikely, Possible, Probable, or Definite) to hPTH 1-34

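### Footnote 9 of the schedule of events limits post-HPTH adverse event reporting to weaning-related events, against Appendix 24.1 section 3.1 and Section 17, and the SAP does not say which scope its tables use

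*Protocol*

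**What the plan says.** Protocol Appendix 24.4, footnote 9, is attached to visit V10 (month 60). For the stabilization phase after HPTH it says: "Only AE/SAEs related to the weaning/termination of HPTH will be reported during this Post HPTH stabilization phase".

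Protocol Appendix 24.1, section 3.1, sets a different scope for the same phase: "All AE/SAEs will be recorded from the time written informed consent is obtained until subject withdrawal" for untreated subjects, "and through the conclusion of the HPTH post-stabilization" phase for treated subjects. It adds: "All AE/SAEs will be captured in CRFs that document the event term", together with severity, relationship and outcome.

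The footnote to the study schema (Appendix 24.3) says: "AE/SAE related to the down titration of HPTH will be reported during this Post-HPTH safety follow-up period". It does not contain the word *only*.

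In the protocol body, Section 8 says: "At each study visit, the study investigator will inquire about the occurrence of any AEs since the last visit". Section 17 has all adverse events summarized for the IRB at continuing review, apart from listed exceptions, and for the FDA at least once a year.

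SAP section 8 re-uses the tables already prepared for the DSMB. SAP section 10 lists several AE tables under the title "Summary of Adverse Events Occurring While on hPTH 1-34 or After Withdrawal from hPTH 1-34", some with a further restriction by investigator period or relatedness. Neither section says which events count after withdrawal.

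**The concern.** Footnote 9 and Appendix 24.1 section 3.1 give two scopes for the same subjects in the same phase. One is all events; the other is only those events that the investigator attributes to weaning or stopping. The filter concerns relation to *withdrawal*, not relation to the drug. Read literally, an event attributed to years of exposure but not to stopping would fall outside it. The study is open-label, so that attribution is made with full knowledge of treatment.

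The completeness of the safety summary is at stake. The SAP tables count events on hPTH and events after withdrawal in one category. A reader cannot tell whether the after-withdrawal part holds all events or a filtered subset. The question became more pressing when the study stopped early, because SAP section 9 says that subjects began to be weaned when new enrollment ended in June 2015. No primary endpoint or efficacy inference is affected.

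**Working it through.** The plan gives no figure to reproduce. The check is a comparison of the passages.

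| Source | Events in scope after HPTH | Restricted to weaning-related? |
|---|---|---|
| Appendix 24.4, footnote 9 (V10) | Reported: weaning or termination related | Yes, explicitly |
| Appendix 24.4, footnote 10 (V11) | Gives visit timing only | No |
| Appendix 24.4, adverse events row | Marked at V10 and V11 | No |
| Appendix 24.3, schema footnote | Down-titration events are reported; silent on others | Unclear |
| Appendix 24.1, section 3.1 | All recorded and entered on CRFs to the end of the phase | No |
| Section 8 | Any event, asked about at each visit | No |
| Section 17 | All summarized to IRB (with exceptions) and FDA | No |
| SAP sections 8 and 10 | On-treatment and after-withdrawal events pooled | Not stated |

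1. *Same phase?* Yes. Footnote 9 and Appendix 24.1 section 3.1 both refer to the stabilization phase. Section 4.6.1 sets its length at a minimum of 3 months (± 2 weeks), and until the subject is stable.

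2. *Can recording and reporting be separated?* One could read Appendix 24.1 as governing what is recorded and footnote 9 as governing what is reported. Section 17 blocks this. Its IRB exceptions are elective, psychosocial and convenience hospitalizations, and expected hypocalcemic symptoms and kidney stones. Events unrelated to weaning are not among them, and the annual FDA summary covers all adverse events. Section 8 and Appendix 24.1 section 3.2 also have clinically significant laboratory findings both recorded and reported as AEs, whatever their association with the product.

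3. *Does another clause settle it?* No. Section 17 lets NIH SOP 16 prevail in a discrepancy, in the context of event definitions and reporting guidelines. It does not say which appendix governs the AE window, and the SOP is not among the documents. Section 8 mentions the end of the AE surveillance period without defining it.

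4. *Size.* Let A be all AE/SAEs in the phase and W those attributed to weaning or termination. If footnote 9 governed what reached the tables, the undercount is A − W. This lies between 0 (every event attributed to weaning) and A (none so attributed). If Appendix 24.1 governed, the undercount is 0. The documents give neither A nor W, nor the number of subjects who entered the phase. Only the direction is known: the filter can lower the after-withdrawal count but cannot raise it.

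**The case against.** The strongest defence is that one schedule footnote stands against Section 8, Section 17 and Appendix 24.1 section 3.1, all of which point to full capture. The CRFs may well be complete. The first part is correct and the second is plausible, but neither removes the contradiction or tells the SAP's reader which scope was used.

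Several stronger readings are tempting, and the documents do not support them:

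- *Late fractures, renal events or bone tumours were lost.* No passage shows that any event was omitted. Unexpected SAEs with a reasonable possibility of relation to the product still go to the FDA under Section 17. A related fatal or life-threatening event, osteosarcoma included, is a halting criterion under Section 15.3. These routes do not, however, bring other events into the AE tables.
- *Two footnotes impose the filter.* Only footnote 9 does. The schema footnote can be read consistently with full capture.
- *The tables compare two periods with unequal ascertainment.* No listed table sets on-treatment events against post-withdrawal events, and none shows post-withdrawal events alone. The possible fault is an incomplete pooled count.
- *Every treated subject is affected up to the 6-month visit.* Only subjects who enter the stabilization phase are concerned. Section 4.6.1 asks for the 6-month visit only after more than 6 months of HPTH, and footnote 10 for that visit carries no AE restriction.

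It is also fair to say that a protocol amendment cannot recover events never collected, and that SAP section 1 reports the safety analyses as already delivered to the DSMB. For that reason the disclosure in the SAP now matters more than the protocol edit.

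**Conclusion.** The inconsistency stands, and it is a stated rule that conflicts with others, not merely a missing detail. Footnote 9 cannot be reconciled with Appendix 24.1 section 3.1 and Section 17, and the SAP is silent on the scope of its after-withdrawal counts. The consequence is conditional. If footnote 9 was followed, the pooled AE tables undercount events after withdrawal by an amount that cannot be derived from the documents. If Appendix 24.1 was followed, the tables are complete but do not say so. The conclusion assumes that footnote 9 means what it says, and that no document outside the protocol and SAP sets the AE window.

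**What to change.** In the protocol, reconcile footnote 9 with Appendix 24.1 section 3.1, so that all AE/SAEs are included through the end of the stabilization phase and relation to weaning is recorded as an attribute. Clarify the schema footnote to match.

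Because enrollment has ended, also add to SAP section 8 a statement of the AE scope that was applied after withdrawal, established from the CRF data and site practice. Then:

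- if all events are on the CRFs, tabulate all of them;
- if the filter was applied at collection, tabulate post-withdrawal events separately and state the filter in the table.

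The cost is two footnotes, a short SAP statement, a check of the CRF data and, at most, a split of the affected tables. Appendix 24.1 section 3.1 already requires the CRF to hold relationship to the product and to the research. Relation to weaning may need one further field, or a derivation from the existing entries.
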